**Table 2-8 Criteria for newly occurring or worsening laboratory parameters**

	Event	Baseline	Post-baseline
Under CTCAE grades	Newly occurring	Grade 0 (normal)	Grade 1 - 4 (any abnormal)
		Missing	Grade 1 - 4 (any abnormal)
	Worsening	Grade 1	Grade 2 - 4
		Grade 2	Grade 3 - 4
Grade 3		Grade 4	
Under normal ranges	Newly occurring	Within normal range	< LLN or > ULN
		Missing	< LLN or > ULN
		< LLN	> ULN
		> ULN	< LLN
	Worsening	BSL < LLN	VALUE < BSL < LLN
		BSL > ULN	VALUE > BSL > ULN
BSL = Baseline value; LLN = Lower limit of normal range; ULN = Upper limit of normal range.			

Participants with any abnormal findings in laboratory values (newly occurring or worsening) will be listed by treatment arm. For parameters with CTCAE definitions, the CTCAE grades will be added in the listing and records with CTCAE grade of 3 or 4 will be flagged.

To evaluate the potential drug-induced hepatotoxicity and renal signal, the liver and renal abnormalities at any time post-baseline will be analyzed by:

- the number and proportion of participants with any newly occurring liver enzyme abnormalities based on each criterion defined in [Table 5-1](#) in Appendix.
- the number and proportion of participants with any renal abnormalities based on each criterion defined in [Table 5-2](#) in Appendix.
- listings of participants with clinically liver or renal abnormality.

## **2.7.4 Other safety data**

### **2.7.4.1 ECG and cardiac imaging data**

#### **2.7.4.1.1 Summary statistics of ECG parameter**

Summary statistics of ECG parameters (PR, QRS, QT, QTcF and RR intervals) recorded centrally will be presented by treatment and visit/time.

#### **2.7.4.1.2 Overall interpretation of the ECGs- ECG findings**

Recording of ECG finding (e.g., prolonged QTc, Torsade de Pointes, Ventricular Tachycardia, etc.) will be sent to Novartis by the central ECG vendor.

ECG findings will be listed by treatment arm and visit/time.

#### **2.7.4.1.3 Clinically significant change in ECG parameters**

The incidence of abnormal ECG diagnosis (see [Table 5-4](#) in appendix) will be presented in terms of count and percentage by treatment arm and by analysis visit.

Participants with abnormal ECG values will be listed by treatment arms and by visit, and the worsening or newly occurring cases will be marked in the listing.

Box plot for change from baseline of QTcF parameter will be provided by treatment arms and by visit.

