- 2. Any prior or current diagnosis of MDD with psychotic features, bipolar disorder, schizophrenia, or schizoaffective disorder as obtained from SCID-5 at screening.
- 3. Participants with acute alcohol or substance use disorder or withdrawal symptoms requiring detoxification, or participants who went through detoxification treatment

- (inpatient or outpatient) within 1 month before Screening, as obtained from SCID-5 at screening.
- 4. Participants with current borderline personality disorder or antisocial personality disorder assessed at Screening, based on DSM-5 criteria and investigator judgment.
- 5. Current clinical diagnosis of autism, dementia, or intellectual disability.
- 6. Participants with a history of suicidal attempt or suicidal behaviour within last year prior to screening and participants presenting suicidal ideation with intent documented by C-SSRS by Yes response to Q4 or Q5 at screening or baseline.
- 7. Participants with evidence of significant renal insufficiency, indicated by an estimated glomerular filtration rate (eGFR) of <40 mL/min/1.73 m2 at screening.
- 8. Use of other investigational drugs at the time of screening, or within 30 days or 5 half-lives of screening, whichever is longer.
- 9. History of hypersensitivity to any of the study treatments or excipients or to drugs of similar mechanism of action (i.e. drugs that affect the NMDA receptor).
- 10. Active hepatitis B virus (HBV), hepatitis C virus (HCV), human immunodeficiency virus (HIV) or active COVID-19 infection as per medical history and/or available medical records.
- 11. History of seizures. Note: childhood febrile seizures are not exclusionary.
- 12. Cardiac or cardiac repolarization abnormality, including any of the following:
 - History of myocardial infarction, angina pectoris, or coronary artery bypass graft within 6 months prior to starting study treatment
 - History of clinically significant cardiac arrhythmias (e.g., ventricular tachycardia), complete left bundle branch block, high-grade atrioventricular (AV) block (e.g., bifascicular block, Mobitz type II and third degree AV block) within 6 months prior to starting study treatment
- 13. Resting QTcF \geq 450 msec (male) or \geq 460 msec (female) at screening or baseline.
- 14. Risk factors for Torsades de Pointes (TdP) including uncorrected hypokalemia or hypomagnesemia, history of cardiac failure, or history of clinically significant/symptomatic bradycardia or any of the following:

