All ECG data will be listed by treatment group, subject and visit/time; abnormalities will be flagged.

The overall interpretation of the ECGs will be summarized by treatment group and visit/time.

Any clinically significant changes in ECG parameters will be summarized by treatment group.

Summary statistics will be provided by treatment and visit/time.

Clinical laboratory evaluations

Notable abnormal laboratory data will be listed by treatment group, participant and visit if ranges are available.

All laboratory data will be summarized by treatment group, and visit/time. Shift tables using the low/normal/high/ (low and high) classification will be used to compare baseline to the worst on-treatment value.

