16.4 Appendix 4: ECG Alert Threshold Values

	Patients 18-30 years	Patients Adult > 30 years *
Resting heart rate Sinus rhythm [bpm]	HR < 30 and a HR decrease ≥ 25% HR > 130	HR < 40 and a HR decrease ≥ 25% HR > 120
QRS duration:		
=> No previous BBB **	> 120 and increase > 25% compared to (predose) baseline	> 120 and increase > 25% compared to (predose) baseline
=> Previous complete BBB * (>120 msec)	> 140 msec	> 140 msec
QTcF	QTcF > 500 msec QTcF increase > 60 msec ***	QTcF > 500 msec QTcF increase > 60 msec ***
Rhythm	Ventricular tachycardia	Ventricular tachycardia
Conduction	New complete heart block (Grade III AV block) Mobitz II AV block	New complete heart block (Grade III AV block) Mobitz II AV block

^{*} Values displayed also correspond to Severe AE ** BBB = Bundle Branch Block *** Normal QTcF with QTc increase > 60 ms may indicate cardiac and non-cardiac pathology, e.g. hypothermia, new BBB, MI. cardiomyopathy or carditis.

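### The by-arm ECG abnormality counts do not separate absolute-limit findings present before dosing from new or worsened ones

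*SAP*

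**What the plan says.** Protocol section 12.5.2, under 12-lead ECG, states the aim: "Any clinically significant changes in ECG parameters will be summarized by treatment group". SAP section 2.7.4.1.3 carries the matching title, "Clinically significant change in ECG parameters". Its count table takes the criteria of Table 5-4 and gives their incidence, which "will be presented in terms of count and percentage by treatment arm and by analysis visit".

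Table 5-4 has two columns:
- **Absolute:** fixed limits. RR below 600 or above 1200 msec; PR below 120 or above 200 msec; QRS below 60 or above 109 msec; QT and QTcF below 320, at or above 450 (male) or 460 (female), and above 500 msec.
- **Relative:** change from baseline. At least 20% either way for RR, PR and QRS; bands of more than 30 to 60 msec and more than 60 msec for QT and QTcF.

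Baseline status enters section 2.7.4.1.3 in one other place, the participant listing, where "the worsening or newly occurring cases will be marked in the listing".

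SAP section 2.7.3 handles laboratory data differently. The general laboratory counts cover newly occurring or worsening parameters, defined against baseline in Table 2-8. The liver summary is "the number and proportion of participants with any newly occurring liver enzyme abnormalities based on each criterion defined in" Table 5-1.

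**The concern.** The absolute rows answer how many participants are beyond a limit at a visit. The section title and the protocol ask how many changed. The two differ whenever someone enters the trial already beyond a limit, and eligibility allows this for RR, PR, QRS and uncorrected QT because no numeric limit is set for them.

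The trial is meant to inform dose selection, and cardiovascular effects are adverse events of special interest. With 14 participants per arm, a few long-standing rate or conduction findings that fall unevenly across arms can look like a drug effect in the by-arm table. They can also make a real new case hard to see.

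**Working it through.** The plan states no figure on this point, so there is none to reproduce. The check is a comparison of the text, followed by an illustration of scale.

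**1. Which rows are affected**
- RR, PR and QRS absolute limits: affected. The RR limits correspond to heart rates of 60000/600 = 100 and 60000/1200 = 50 beats per minute.
- Uncorrected QT absolute limits: affected, since eligibility refers to QTcF only.
- QTcF high limits: largely unaffected. Exclusion criterion 13 removes QTcF of 450 (male) or 460 (female) msec or more at screening or baseline.
- All Relative rows: unaffected, since they are defined against baseline.

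**2. Whether such participants can enter**

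Exclusion criterion 12 covers recent cardiac or repolarization abnormality, with examples that include clinically significant arrhythmia and "complete left bundle branch block, high-grade atrioventricular (AV) block". Criterion 14 covers clinically significant or symptomatic bradycardia, and criterion 21 leaves room for investigator judgement. None sets a numeric PR, QRS or RR limit. A mildly long PR, a QRS just above 109 msec or a slow heart rate without symptoms can therefore be present at entry.

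**3. Whether another part of the table recovers the information**
- A baseline row: SAP Table 2-3 lists Baseline as an ECG analysis visit, so one may appear. If an arm shows two participants at baseline and two at 4 hours, these could be the same two people or four different ones.
- The Relative rows: they catch only large shifts. A PR of 205 msec rising to 240 msec is a change of 35/205 = 17%, below the 20% threshold. It would count in the absolute row at both times and never in the relative row.

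**4. Scale**

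Inputs: n = 14 per arm (protocol section 12.8.1, SAP section 3); five post-dose ECG time points (0.5, 1.5, 4 and 24 hours, and Day 29; protocol Table 8-1); p = the proportion meeting one absolute criterion before dosing. The documents do not give p, so a range is assumed.

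- One participant: 1/14 = 7.1% of an arm, at each of the five time points if the finding persists.
- At least one such participant in a given arm: 1 − (1 − p)^14.
- At least one of the three active arms exceeds placebo by two or more with no drug effect: Σₓ P(X = x) · [1 − F(x + 1)³], where X is Binomial(14, p) and F is its cumulative distribution.

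For p = 5%:
- P(X = 0, 1, 2) = 0.4877, 0.3593, 0.1229
- F(1), F(2), F(3) = 0.8470, 0.9699, 0.9958
- 0.4877 × (1 − 0.8470³) + 0.3593 × (1 − 0.9699³) + 0.1229 × (1 − 0.9958³) = 0.191 + 0.031 + 0.002 = 0.224

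| Assumed p | Expected per arm (14p) | At least one in an arm | Some active arm exceeds placebo by ≥2 |
|---|---|---|---|
| 2% | 0.28 | 25% | 7% |
| 5% | 0.7 | 51% | 22% |
| 10% | 1.4 | 77% | 36% |

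The last column is for one criterion and assumes that each finding persists at the time point shown.

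**The case against.** The strongest reply is that the reader is not misled. The table runs by analysis visit and Baseline is one of those visits. By contrast, the vital-sign count in section 2.7.4.2 is expressly limited to post-baseline visits. A baseline row would show any imbalance, the Relative rows count change by arm, the listing marks new and worsening cases, and the ECG parameters are also summarized by visit. The SAP does not state outright that pre-existing cases are counted; that is inferred from the absence of a condition. It also does not say whether the Absolute and Relative columns are reported separately, although the separate msec bands for QT and QTcF suggest that they are.

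Much of this stands and limits the point. It does not remove it, because no planned output gives the number of new cases of an absolute criterion by arm.

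Three stronger readings are tempting and are not supported:
- **That the plan ignores change from baseline in the ECG.** The Relative column measures it.
- **That eligibility removes nothing but complete left bundle branch block and high-grade AV block.** Criteria 12, 14 and 21 are broader, and Table 8-1 requires the investigator to find the pre-dose ECG satisfactory before dosing.
- **That the SAP breaks a rule it applies everywhere else.** The absolute vital-sign limits carry no newly-occurring restriction either. Protocol Appendix 4, which ties a QRS alert to "> 120 and increase > 25% compared to (predose) baseline", sets alert thresholds and not an analysis rule; some of its other entries have no baseline condition.

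**Conclusion.** The point holds in a limited form. As written, the absolute-criterion rows for RR, PR, QRS and uncorrected QT mix pre-existing findings with new ones, and the new or worsening status that would separate them is confined to a listing.

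The size depends on a prevalence that the documents do not give. The chance of a spurious excess of two or more participants in some active arm runs from about 7% to 36% as p goes from 2% to 10%, and at the low end the issue is minor. A reader might infer that the table is likely to suggest a false dose-response, but the calculation does not show that. It counts an excess in any active arm, and a pattern rising in order from placebo to 10 mg is a narrower event.

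The consequence is confined to a descriptive safety table in a non-confirmatory trial. No primary result or decision rule uses it. The change is still worth making, because it is nearly free and brings the table into line with its title and with protocol section 12.5.2.

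**What to change.** In SAP section 2.7.4.1.3, for each absolute criterion in Table 5-4, tabulate by arm and post-dose time point:
- participants newly meeting the criterion, meaning it was not met at baseline, with a missing baseline counted as new, as in Table 2-8;
- in a separate row, participants who met it at baseline and worsened;
- the number meeting it at baseline, and the denominator used.

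A baseline to post-dose shift table for each criterion would serve equally well. The worsened row is needed because a count of new cases alone would drop someone such as the participant whose PR goes from 205 to 240 msec. Keep the Relative rows as they are, and state that the two columns are reported separately.

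The cost is a few sentences of SAP text and some extra table rows. The new or worsening flag is already needed for the listing, so no further data are required.

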### **2.7.4.2 Vital signs**

The analyses of vital signs (body temperature, systolic/diastolic blood pressure, pulse rate) and weight will include summary statistics for both the original measures (averaged means of three measures) and the change from baseline by treatment arm and by analysis visit. Boxplot and Mean $\pm$ SD line plot of the change from baseline of blood pressure (SBP and DBP) over time will be provided by treatment arm.

The number and percentage of participants with clinically relevant abnormality (see [Table 5-3](#) in appendix) at any post-baseline visit will be presented.

Participants with clinical relevant abnormality and any abnormal findings (worsening or newly occurring) will also be flagged in listings.

### 2.7.4.3 Clinician Administered Dissociative States Scale

The Clinician Administered Dissociative States Scale (CADSS) is a questionnaire that assesses dissociative effects might related to MIJ821. The CADSS comprises 23 subjective items and participant's responses are coded on a 5-point scale (0=" Not at all", 1=" Mild", 2="Moderate", 3="Severe" and 4="Extreme") based on their current experience. The CADSS will be assessed at baseline (Day 1, -1 hour pre-dose), 0.5 hour, 1.5 hour and 4-hour post-dose on Day 1, and follow-up assessments at Day 2 (24-hour), Day 8, Day 15, Day 22 and Day 29.

The CADSS can be divided into 3 components using the following scoring method defined in [Table 2-9](#). A higher score represents a more severe condition. Missing data at any subjective item will be unlikely since the items could not be skipped during the interview unless raters provide rationales, in which case the component scores and the total score will be calculated based on the proration approach. Specifically, if the percentage of missing items is more than 10% of the total number of items for the component score, no imputation will be made and the component score will be missing. Otherwise, the sum of available items will be used and the component score is calculated as follows:

$$\text{Component score} = \text{Sum of scores from items present} * (\text{total number of items in the component} / \text{number of items present}).$$

**Table 2-9 CADSS components and total scales**

Component	Questions	Range
Depersonalization	Sum of 3, 4, 5, 6, 7, 20, 23	0-28
Derealization	Sum of 1, 2, 8, 9, 10, 11, 12, 13, 16, 17, 18, 19, 21	0-52
Amnesia	Sum of 14, 15, 22	0-12
Total Score	Sum of 1 through 23	0-92

For the total score and each component score (depersonalization, derealization and amnesia), the summary table of original measures and change from baseline values will be provided by treatment arm and analysis visit. The component scores for patients with CADSS total score >0 at any post-dose visit will be listed. Boxplots will also be provided for change from baseline values for the total score over time by treatment arms.

In addition, the number and percentage of participants satisfying the following criteria will be summarized separately by treatment arms and by analysis visit.

- CADSS total score > 4 and change from baseline > 0.
- Change from baseline in CADSS total score > 4.

### 2.7.4.4 Modified Observer's Assessment of Alertness/Sedation

The Modified Observer's Assessment of Alertness/Sedation (MOAA/S) will be used to assess participant responsiveness and measure sedation associated with MIJ821. The MOAA/S scores

range from 0 [No response to painful stimulus] to 5 [Readily responds to name spoken in normal tone (awake)]. A lower score of MOAA/S indicates more severe condition of sedation.

The MOAA/S will be taken at the same visits and time points as CADSS. The following summary table and/or plots will be provided:

- A stacked bar plot for categorical MOAA/S score by treatment arm and analysis visit.
- Summary table and bar-plot comparing the percentage of participants with any sedation (MOAA/S≤4) across treatment arms over time.
- Summary table and bar-plot comparing the percentage of participants with severe sedation (MOAA/S≤2) across treatment arms over time.

#### 2.7.4.5 Columbia-Suicide Severity Rating Scale

The Columbia-Suicide Severity Rating Scale (C-SSRS) is a questionnaire that prospectively assesses suicidal ideation and behavior (SIB) and non-suicidal self-injurious, as well as intensity assessments for suicidal ideation, as summarized in [Table 2-10](#) below. The 11 preferred SIB categories include five levels of suicidal ideation, five levels of suicidal behavior and the category non-suicidal self-injurious. Each category has a binary response (yes/no). For this study, participants who have suicidal ideation with intent (answered ‘Yes’ for question 4 or 5) at baseline will be excluded from the study as screening failure.

The C-SSRS will be assessed at Screening, Baseline (Day 1, -1 hour pre-dose), 4-hour post-dose on Day 1, and follow-up visits at 24 hour (Day 2), Day 8, Day 15, Day 22 and Day 29 (EOS). The SIB assessments obtained during screening will be based on participant’s experience during lifetime and past 1 month. All follow-up visits will be based on participant’s experience since last visit.

The analysis for this scale will be based on the SAF. No safety cut-off will be applied for the SIB data reporting, i.e., all collected data will be used in the analysis.

Patients who answered “yes” to each question in [Table 2-10](#) will be counted by treatment arm and by visit. The descriptive statistics will be provided for the suicidal ideation score (the most severe suicidal ideation) by treatment arm and by visit.

Suicidal ideation and behavior data will be listed. Detailed answers to C-SSRS items will be listed separately for subjects with any suicidal ideation at any time post-baseline (i.e., a ‘yes’ answer to at least one of the five suicidal ideation questions at any time post-baseline) and for a subject with any suicidal behavior at any time post-baseline (i.e., a ‘yes’ answer to at least one of the five suicidal behavior questions at any time post-baseline).

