1.1 Background

1.1.1 Treatment resistant depression

Depression is a serious and life-threatening condition with high rates of morbidity and a chronic disease course. It is a common illness worldwide, with more than 264 million people affected (WHO 2020). When long-lasting and with moderate or severe intensity, depression causes the affected person to suffer greatly, impairing the ability to work, self-care, and maintain relationships.

Despite a broad availability of antidepressant medication, about a third of patients suffering from MDD fail to respond fully to antidepressant treatment of adequate duration and dose, and the majority fail to maintain long-term response to standard antidepressants (Rush et al 2006). This chronicity of symptoms predisposes patients to treatment resistance.

Treatment-resistant depression (TRD) is defined as a lack of clinically meaningful improvement after treatment with at least 2 different antidepressant agents prescribed in adequate dosages for adequate durations.

Patients suffering from TRD are very likely to have suicidal ideation and experience a disproportionate burden of illness causing significant impairment and increased morbidity (Shelton et al 2010).

Therefore, there is a high unmet medical need for rapid-acting antidepressants that are either more effective or better tolerated, treatments that can effectively interrupt a depressive episode and are able to prevent future depressive episodes.

Ketamine, which is a N-methyl-D-aspartate (NMDA) receptor antagonist, has been shown to be effective in TRD in off-label research, but is limited by psychotomimetic side effects (Katalinic et al 2013, Browne and Lucki 2013). Further, ketamine has been shown to be rapid-acting and reduce suicidality (Katalinic et al 2013). The efficacy of ketamine provides the rationale for targeting N-methyl-D-aspartate (NMDA) receptor inhibition as a rapid-onset antidepressant mechanism.

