- There is no increase in suicidal intensity or new occurrence of suicidal ideation as assessed by C-SSRS
- No clinically relevant QTcF prolongation (QTcF≥500 msec or increase in QTcF from baseline≥60 msec)
- No clinically relevant abnormalities in blood pressure (BP) (90≤Sysotlic BP (SBP) ≥180 mmHg or 50≤Diastolic BP (DBP) ≥105 mmHg or increase or decrease in SBP of at least 20 mmHg or increase or decrease in DBP of at least 15 mmHg from baseline) or any increase in BP that is accompanied by symptoms, such as headache, dizziness, nausea, visual disturbances or other neurological symptoms
- The investigator does not identify any other AEs that require continued monitoring

If the participant cannot be released from the clinical site 4 hours after dosing, extended safety monitoring will be performed as described below.

The post-dose follow-up period will continue for 4 weeks (28 days) after treatment. On-site visits to assess efficacy and safety are scheduled on Day 2 (24 hours post-dose) and subsequently every week (i.e., on Days 8, 15, 22 and 29) during the follow-up period. The assessment to address the primary objective will be performed at Day 2 (24 hours post-dose). Phone calls will be conducted 3 days after each on-site visit with the exception of End-of-study (EOS) visit. The EOS visit will be completed on site on Day 29. The total duration of the study is approximately 8 weeks (56 days), including screening.

Extended safety monitoring in case of AEs on Day 1 (4 hours after dosing)

If extended monitoring is required beyond the minimum 4 hours of monitoring on Day 1, the following will be assessed:

- Monitoring of CNS adverse events (dissociation, amnesia, sedation):
 - If there are any dissociative AEs, amnesia or somnolence/sedation present, the participant should be monitored at the clinical site until these AEs are fully resolved. If the dissociative AEs or cognitive symptoms do not resolve within 6 hours after onset, the participant will be required to stay at the clinical site for overnight monitoring and can be discharged after the assessments are completed on Day 2 and the AEs have resolved. The onset and resolution time of dissociative and cognitive AEs should be captured as accurately as possible. The following assessments are recommended to follow CNS AEs, whenever possible (e.g., participant is awake):

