The C-SSRS is a questionnaire that prospectively assesses suicidal ideation and suicidal behavior. The C-SSRS will be administered as defined in Section 8. In this study, the following recall periods will be used: "one month/one year" and "since last evaluation". Further details on the C-SSRS procedure are given in Section 10.2.4.

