10.2.4 Prospective suicidality assessment

The C-SSRS is a questionnaire that prospectively assesses suicidal ideation and suicidal behavior. The C-SSRS must be administered as defined in the Visit schedule (Section 8).

The C-SSRS, which uses a semi-structured interview to probe participant responses, will be administered by an individual who has received training and certification in its administration. At the first study visit, the "baseline/screening" version of the C-SSRS will be administered. This version assesses suicidal ideation and suicidal behavior during the participant's last one year and during a predefined period of one month. At subsequent visits, the "since last visit" version will be administered.

If, at any time after screening and/or baseline (i.e., prior to randomization), the score is "yes" on item 4 or item 5 of the suicidal ideation section of the C-SSRS or "yes" on any item of the suicidal behavior section, the participant should be screened failed and adequate treatment and management should be provided as per standard of care.

In addition, all life-threatening events must be reported as SAEs. For example, if a participant answers "yes" to one of the questions in the suicidal behavior section, an SAE must be reported if the event was life-threatening. All events of "Non-Suicidal Self-Injurious Behavior" (question also included in the suicidal behavior section) should be reported as AEs and assigned the appropriate severity grade.

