### 2.7.3 Laboratory data

Both of raw measures and change from baseline of laboratory results (hematology, blood chemistry) will be summarized by treatment arm and analysis visit.

The clinical abnormality is defined as out of the normal ranges defined in the laboratory specification document. The newly occurring and worsening events are defined by comparing the measured laboratory parameters at baseline and post-baseline with the lower and/or upper limits of the normal ranges (see [Table 2-8](#)). In addition to the normal ranges, some of the lab parameters, which are covered by the Common Terminology Criteria for Adverse Events (CTCAE) version 5.0, will also be graded using the Novartis internal validated macro (with details covered in PDS) and the newly occurring and worsening events are also defined in [Table 2-8](#). The number and proportion of participants with newly occurring or worsening laboratory parameters based on normal ranges and CTCAE grades (if applicable) will be summarized by treatment arms and by visits (24 hours post-dose and EOS).

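### The planned C-SSRS summaries cannot separate new or worsened ideation from persistent ideation at items 1–3, which eligibility allows at dosing

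*SAP*

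**What the plan says.** SAP 2.7.4.5 plans two C-SSRS summaries. Participants answering yes to each question in Table 2-10 "will be counted by treatment arm and by visit". For the ideation score, "The descriptive statistics will be provided for the suicidal ideation score (the most severe suicidal ideation) by treatment arm and by visit". The section also lists the ideation and behaviour data, with item-level answers for anyone with post-baseline ideation or behaviour. It states no shift, new-onset, worsening or change-from-baseline summary, and no count at any time post-dose.

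On who may enter, exclusion criterion 6 in Protocol 5.2 removes participants with a yes to question 4 or 5 at screening or baseline, and those with an attempt or suicidal behaviour in the year before screening. Protocol 10.2.4 adds that a yes on item 4, item 5 or any behaviour item before randomization is a screen failure. Neither section excludes ideation at items 1–3. Protocol 1.1.1 says of the disease generally: "Patients suffering from TRD are very likely to have suicidal ideation".

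On recall, Protocol 8.5.1.1 gives the periods as "one month/one year' and 'since last evaluation". Protocol 10.2.4 says: "At subsequent visits, the 'since last visit' version will be administered". SAP 2.7.4.5 uses the period since the last visit for all follow-up readings, and lifetime plus the past month for screening.

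**The concern.** Suicidality is an adverse event of special interest (Protocol 10.2.5), and the C-SSRS is a named secondary safety measure (Protocol Table 2-1). The safety question is whether ideation appears or gets worse after the injection. The protocol frames it that way for release on Day 1, where the criterion is: "There is no increase in suicidal intensity or new occurrence of suicidal ideation as assessed by C-SSRS". A count of everyone with ideation at a visit answers a different question, because it mixes participants who had it before dosing with those who did not.

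Elsewhere the SAP does make the comparison with baseline. For laboratory data, "The newly occurring and worsening events are defined by comparing the measured laboratory parameters at baseline and post-baseline". The CADSS counts in SAP 2.7.4.3 require a change from baseline. The C-SSRS has no such rule. With small arms, a chance difference in pre-existing ideation carries straight into the by-visit counts. It could look like a drug effect or hide one.

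**Working it through.** There is no planned figure to reproduce; the sample size calculation does not concern this scale.

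**Inputs.** Arm size n = 14 (Protocol 12.8.1, SAP 3). Eligibility from Protocol 5.2 and 10.2.4. Item numbering from SAP Table 2-10. Baseline prevalence of ideation at items 1–3 is not given; 10% to 70% is assumed.

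**Step 1. Which items can be yes before dosing in an eligible participant?**

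| Items | Pre-dose yes possible? | What a post-dose yes means |
|---|---|---|
| 1–3, ideation without intent | Yes | Persistent, new or worsened: not separable |
| 4–5, ideation with intent | No | New |
| 6–10, suicidal behaviour | No | New |

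New here means relative to the required pre-dose assessments, not to lifetime history. Item 11 (non-suicidal self-injury) is less clear. Protocol 10.2.4 places the question in the behaviour section, while SAP Table 2-10 lists it apart.

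**Step 2. What do the counts tell us about new cases?** With y0 yes at baseline and y1 yes at a visit, the number newly yes lies between max(0, y1 − y0) and min(y1, n − y0).

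| y0 | y1 | New cases possible | At risk (14 − y0) |
|---|---|---|---|
| 4 | 4 | 0 to 4 | 10 |
| 7 | 7 | 0 to 7 | 7 |
| 10 | 10 | 0 to 4 | 4 |
| 0 | 2 | exactly 2 | 14 |

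The first three rows illustrate items 1–3: even with baseline shown, the counts do not fix the number of new cases. The last row illustrates items 4–10, where y0 = 0 and the planned count is the new-onset count.

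The ideation score behaves the same way. If one participant moves from category 1 to 3 and another in the same arm from 3 to 1, the arm's score distribution is unchanged although one participant has worsened.

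**Step 3. How large is chance imbalance at baseline?** Take the counts in two arms, X and Y, as independent Bin(14, p). The SD of the difference in proportions is √(2p(1 − p)/14). P(|X − Y| ≥ 3) is summed exactly.

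| p (assumed) | SD of difference, percentage points | P(3 or more participants apart) |
|---|---|---|
| 0.1 | 11.3 | 0.11 |
| 0.2 | 15.1 | 0.23 |
| 0.3 | 17.3 | 0.30 |
| 0.5 | 18.9 | 0.34 |
| 0.7 | 17.3 | 0.30 |

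**Step 4. Recall at 4 h and at screening.** Protocol Table 8-1 puts the −1 h and 4 h readings under one visit number. A form asking about the time since the last evaluation would cover the hours since −1 h. A form asking about the time since the last visit could be read as reaching back before Day 1. A new-onset count at 4 h depends on which reading applies. At screening, the protocol's one month and one year differ from the SAP's lifetime and past month.

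**The case against.** Several counter-arguments have weight.

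- *A reader might infer that the table cannot show new or worsened suicidality at all.* The documents do not support that. Step 1 shows that items 4–10, the most serious categories, are covered, and a move from items 1–3 into intent or behaviour is visible.
- *Baseline may be tabulated.* It is an analysis visit in SAP Table 2-1, and nothing limits the by-visit counts to post-dose visits. This would display a baseline imbalance, but Step 2 shows that it would not identify who is new.
- *The standard output is not public.* The SAP change log says the C-SSRS summary moved to a standard table and listing. A shift table in the shells cannot be excluded. If there is one, a sentence in SAP 2.7.4.5 would settle the matter.
- *Individual change can be read from the listings, and new or worsened events reach the AE and AESI tables* (SAP 2.7, 2.7.1.2). Both are true. However, the listings leave the comparison to be made by hand across about 56 participants, and Protocol 10.2.5 only recommends recording clinically significant scale findings as events. Neither replaces a systematic table.
- *High baseline ideation is not established.* The statement in Protocol 1.1.1 describes the disease generally, not this restricted population. Protocol Table 4-1 reports a median ideation score of 0 in every arm of the proof-of-concept study. Those were post-dose readings on another scale, but they are reason to carry the range down to 10% and not to claim that imbalance will dominate.
- *A reader might extend the point to the ECG table*, where incidence "will be presented in terms of count and percentage by treatment arm and by analysis visit". That is largely met already: SAP Table 5-4 includes changes relative to baseline, and SAP 2.7.4.1.3 marks new or worsening cases in the listing.
- *The recall phrases can be reconciled*, one naming the period and the other the form version. That is a fair reading, and no passage says the 4 h form reaches back to screening. The wording still permits both readings.

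**Conclusion.** The point holds for ideation items 1–3, including worsening within them. The C-SSRS summaries stated in the SAP do not condition on the pre-dose answer, so at these items they cannot distinguish new or worsened ideation from ideation that persists. Items 4–10 are unaffected in eligible participants.

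The size depends on a prevalence that the documents do not give. Over the assumed range, a baseline gap of 3 or more participants between two arms arises by chance in roughly 1 comparison in 9 (p = 0.1) to 1 in 3 (p = 0.5). The calculation treats the arms as independent binomial samples. The trial is non-confirmatory and its safety summaries are descriptive, so no test result is at risk; what suffers is the reading of a special-interest safety signal. The inconsistent recall wording is a separate, smaller fault that would carry into any new-onset count at 4 h.

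**What to change.** In SAP 2.7.4.5, keep the raw counts and state that baseline is shown as a column. Add a table by arm, at each post-dose visit and at any time post-dose, of participants with:

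- (a) new ideation: none at the −1 h assessment, any post-dose;
- (b) worsened ideation: maximum post-dose category above the −1 h category, reported among those with ideation at −1 h so that it does not overlap with (a).

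A shift table of maximum ideation category would serve both.

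Align the recall wording in Protocol 8.5.1.1, Protocol 10.2.4 and SAP 2.7.4.5, for the 4 h form and for the screening look-back, and state which form versions were actually used. No change to the ECG outputs is needed on this account.

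The cost is one table from data already collected and a few aligned phrases.
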